### **9.7.2. Cohorts 2a and 2b**

The participants in Cohorts 2a and 2b will not have completed the planned vaccination schedule by the time of unblinding, because the booster vaccinations will not yet have occurred.

For safety, efficacy, and immunogenicity, the same analysis strategy will be applied as for Cohorts 1a, 1b, and 3.

[figure not shown]
Analyses pertaining to the booster vaccinations will be produced as planned. The analyses will include all available participants who have followed the vaccination schedules as per the study design (ie, did not receive an unscheduled vaccination). Note that the post-booster safety or efficacy analyses will not include participants who were unblinded at their own request, since they are likely to be completely unblinded (implying they would know in advance whether they would receive active vaccine or placebo at each of the booster time points). Participants who continue with the booster vaccinations and all study procedures as described in the SoA, will be included in the immunogenicity analysis.

The analysis strategy is depicted graphically in [Figure 10](#).

---

a Unscheduled vaccination: for placebo participants: a single dose of  $5 \times 10^{10}$  vp Ad26.COV2.S offered at the study site or an authorized/licensed COVID-19 vaccine offered outside of the study; for participants in the active vaccine groups: an authorized/licensed COVID-19 vaccine offered outside of the study.

Figure 10: Analysis strategy after unblinding, depicted by scenario

AESI adverse event of special interest; C cohort; SAE serious adverse event

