#### **Analyses after Unblinding all Participants Following Emergency Use Authorization (EUA) or Approval in any Country**

In general, after unblinding, participants who received placebo only during primary regimen, can elect to receive a single dose of  $5 \times 10^{10}$  vp Ad26.COV2.S offered at the study site, can opt to receive an authorized/licensed COVID-19 vaccine outside of the study, or may choose not to receive any additional vaccinations. Participants who received active vaccine will be asked to continue the study or can opt to receive an authorized/licensed COVID-19 vaccine outside of the study.

The participants in cohorts 1a, 1b, and 3 have completed the planned study vaccination regimen by the time of unblinding (or have discontinued earlier). Participants in Cohorts 2a and 2b will not have completed the planned vaccination schedule by the time of unblinding, because the booster vaccinations will not yet have occurred.

The safety and efficacy analyses will be censored at the date of unblinding or the receipt of an unscheduled vaccineb, whichever event occurs first. SAEs reported after unblinding or receipt of an unscheduled vaccine, whichever comes first, will be listed.

The immunogenicity analyses will be censored at the date of the receipt of an unscheduled vaccine. Immunogenicity samples taken after the receipt of an unscheduled vaccine will be included in the listings and flagged.

Analyses pertaining to the booster vaccinations in Cohorts 2a and 2b will be produced as planned. Post-booster safety or efficacy analyses will not include participants who were unblinded at their own request, nor participants who received an unscheduled vaccination.

---

a Following local approval of protocol Amendment 15, participants who received an authorized/licensed COVID-19 vaccine outside of the study are allowed to receive a single ad hoc booster dose of Ad26.COV2.S vaccine ( $5 \times 10^{10}$  vp) if the last vaccination was  $\geq 6$  months ago.

b Unscheduled vaccine: for placebo participants: a single dose of  $5 \times 10^{10}$  vp Ad26.COV2.S offered at the study site or an authorized/licensed COVID-19 vaccine offered outside of the study; for participants in the active vaccine groups: an authorized/licensed COVID-19 vaccine offered outside of the study.

The analysis strategy is depicted graphically in the figure below.

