## **7. DISCONTINUATION OF STUDY VACCINATION AND PARTICIPANT DISCONTINUATION/WITHDRAWAL**

### **7.1. Discontinuation of Study Vaccination**

Study vaccinations will be withheld for the reasons listed below. These participants must not receive any further doses of study vaccine but should remain on study for follow-up with assessments of safety and immunogenicity. Additional unscheduled visits may be performed for safety/reactogenicity reasons, if needed. In case of questions, the investigator is encouraged to contact the sponsor.

- Any related AE, worsening of health status or intercurrent illnesses that, in the opinion of the investigator, requires discontinuation from study vaccine
- The participant becomes pregnant
  - Note: Applicable to the US only: Following local approval of Protocol Amendment 15, participants who are pregnant may receive booster vaccination with Ad26.COV2.S, if allowed by local regulations and if the investigator considers that the potential benefits outweigh the potential risks to the mother and fetus (see Section 8.7).
- Unblinding on the participant level that, in the opinion of the sponsor, would compromise the integrity of the data
- The participant received an authorized/licensed COVID-19 vaccine outside of the study.
  - Note: following local approval of protocol Amendment 15, eligible participants (see Section 8.7) are allowed to receive a single ad hoc booster dose of Ad26.COV2.S vaccine ( $5 \times 10^{10}$  vp) if the last vaccination was  $\geq 6$  months ago.
- Anaphylactic reaction following vaccination, not attributable to causes other than vaccination
- SAE or other potentially life-threatening (Grade 4) event that is determined to be related to study vaccine
- Chronic or recurrent use of systemic corticosteroids and administration of antineoplastic and immunomodulating agents or radiotherapy
- Withdrawal from further study vaccination
- Participant has a positive test result for SARS-CoV-2 infection during the study (see Section 8.1.2). Note: participants may receive a placebo crossover vaccination or ad hoc booster vaccination with the Ad26.COV2.S vaccine after they have recovered from the acute illness and at least 3 months have passed as specified in Sections 8.6 and 8.7.
- Participant receives any experimental medication (including experimental vaccines other than the study vaccine) or receives a COVID-19 treatment
- Participant previously experienced TTS, or heparin-induced thrombocytopenia (HIT) or GBS.

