#### **8.6. Assessments and Procedures after EUA or Approval in any Country**

Following EUA, conditional licensure, or approval in any country for the single-dose regimen of  $5 \times 10^{10}$  vp Ad26.COV2.S, all participants from countries where Amendment 10 is approved locally by the Health Authority and IEC/IRB, will be unblinded to disclose who received placebo only during primary regimen.

The Procedures detailed in this section also apply to participants who were unblinded at their own request prior to Amendment 10.

In general, after unblinding, participants who initially received placebo only, can elect to receive a single dose of  $5 \times 10^{10}$  vp Ad26.COV2.S offered at the study site (ie, placebo crossover vaccination), can opt to receive an authorized/licensed COVID-19 vaccine outside of the study, or may choose not to receive any additional vaccinations. Participants who received active vaccine will be asked to continue in the study or can opt to receive an authorized/licensed COVID-19 vaccine outside of the study.

All currently enrolled participants will be contacted by the study site to inform them whether they received active vaccine or placebo only. Participants will be counseled regarding the importance to continue practicing preventative measures to limit the spread of the disease including social

distancing, wearing face masks, and frequent hand washing, in compliance with local and national guidelines. This contact will be documented in the source documents.

Participants in the active vaccine groups will be informed they received at a minimum the dose level approved for Emergency Use (single-dose regimen of  $5 \times 10^{10}$  vp Ad26.COV2.S) and will be asked to continue to be followed in this study in line with the [Schedule of Activities \(SoA\)](#). For participants who were unblinded (at any time) and did not receive an authorized/licensed COVID-19 vaccine outside of the study, they will be permitted to receive the Cohort 2 booster vaccinations. If they opt to receive an authorized/licensed COVID-19 vaccine outside of the study, they will be discontinued from further study vaccination (see Section [7.1](#)).

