### **Interim and Primary Analyses for Cohort 2**

An interim analysis for Cohort 2 will be performed when 28-day safety data is collected for approximately 270 participants after the first study vaccination. This safety analysis may be required as the basis for enrollment of adults aged  $\geq 18$  to  $\leq 55$  years in subsequent larger studies. It will also include available immunogenicity data for seronegative participants (VNA and ELISA).

The primary analysis for Cohort 2 will include all available safety data for approximately 270 participants through 28 days after completion of the second study vaccination in the 2-dose primary regimen. It will also include available immunogenicity data for seronegative participants (VNA and ELISA).

Interim analyses of the data from each booster vaccination will be performed after the last participant receives their respective booster vaccination and will include all available safety and immunogenicity data up to 28 days after the vaccination. These interim analyses will present the data in a group-level unblinded fashion, as follows:

- The interim analysis of the first booster vaccination (at 6 months for Cohort 2a or at 8 months for Cohort 2b), will keep the groups 1, 3, and 4 pooled.
- The interim analysis of the second booster vaccination (at 12 months for Cohort 2a or at 14 months for Cohort 2b), will keep the groups 1 and 4 pooled.

This stepwise group-level unblinding approach avoids indirect unblinding of individual participants who have yet to receive the active (or last) booster (eg, due to rare or unique events).

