### **End-of-study Analysis**

The end-of-study analysis will be performed when all included participants have completed the last visit or last booster vaccination follow-up visit or discontinued the study earlier.

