## **9.7. Analyses after Unblinding all Participants Following EUA or Approval in any Country**

### **9.7.1. Cohorts 1a, 1b, and 3**

The participants in these cohorts have completed the planned study vaccination regimen by the time of unblinding (or have discontinued earlier). In general, after unblinding, participants who received placebo only during primary regimen, can elect to receive a single dose of

a Following local approval of protocol Amendment 15, participants who received an authorized/licensed COVID-19 vaccine outside of the study are allowed to receive a single ad hoc booster dose of Ad26.COV2.S vaccine ( $5 \times 10^{10}$  vp) if the last vaccination was  $\geq 6$  months ago.

$5 \times 10^{10}$  vp Ad26.COV2.S offered at the study site, can opt to receive an authorized/licensed COVID-19 vaccine outside of the study, or may choose not to receive any additional vaccinations. Participants who already received active vaccine will be asked to continue the study or can opt to receive an authorized/licensed COVID-19 vaccine outside of the study.

The safety analyses will be censored at the date of unblinding or the receipt of an unscheduled vaccinea, whichever event occurs first. SAEs and AESIs reported after unblinding or receipt of an unscheduled vaccine, whichever comes first, will be listed.

The immunogenicity analyses will be censored at the date of the receipt of an unscheduled vaccine. Immunogenicity samples taken after the receipt of an unscheduled vaccine will be included in the listings and flagged. Samples obtained from unblinded participants who do not get any further vaccination, will not be censored from the analyses.

Efficacy analyses will be censored at the date of unblinding or the receipt of an unscheduled vaccine, whichever comes first.

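### The Cohort 2 post-booster safety and efficacy analyses exclude anyone with an unscheduled vaccination, without requiring that it came before the booster

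*Protocol*

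**What the plan says.** For the booster part of Cohort 2, section 9.7.2 admits participants "who have followed the vaccination schedules as per the study design (ie, did not receive an unscheduled vaccination"). The synopsis puts it as an exclusion: "Post-booster safety or efficacy analyses will not include participants who were unblinded at their own request, nor participants who received an unscheduled vaccination". For active-vaccine recipients, the footnotes define an unscheduled vaccine as an authorised or licensed COVID-19 vaccine obtained outside the study. The definition carries no date.

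Other sections handle the same event by date. Section 9.7.1 states "The safety analyses will be censored at the date of unblinding or the receipt of an unscheduled vaccine", whichever comes first, and 9.7.2 says that the same strategy applies to Cohort 2. Section 9.8 likewise makes the ad hoc booster a reason for censoring data, not for removing the participant.

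On conduct, section 8.6 says of active recipients: "If they opt to receive an authorized/licensed COVID-19 vaccine outside of the study, they will be discontinued from further study vaccination". Section 7.1 keeps such people under observation: "These participants must not receive any further doses of study vaccine but should remain on study for follow-up with assessments of safety and immunogenicity".

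**The concern.** A participant who takes an outside vaccine first should not receive the scheduled booster at all, because sections 7.1 and 8.6 stop it. Among people who were actually boosted, the exclusion therefore acts almost only on those vaccinated outside afterwards. These participants remain on study, and their solicited (7-day) and unsolicited (28-day) booster data may already be complete.

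Membership of a booster safety table then depends on something the participant does after the booster reactions have been observed. At stake is a smaller, and possibly selected, denominator in groups planned at 30. A table for a given booster could also change with the date on which it is run.

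**Working it through.** **1. Follow one participant through the rules.** Take Group 2 of Cohort 2a (Tables 2 and 6).

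- The active booster is due on Day 183, the 7-day visit on Day 190 and the 28-day visit on Day 211. The next injection, a placebo, is due on Day 366.
- Suppose an outside vaccine is taken after Day 211. Sections 7.1 and 8.6 cancel the Day 366 injection but keep the participant on study.
- Under the inclusion sentence in 9.7.2, the participant has received an unscheduled vaccination and is out of the booster safety analysis, with all data from Day 183 to Day 211.
- Under censoring at the date of the outside vaccine, all of those data stay in.

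**2. Check whether the shared strategy in 9.7.2 repairs this.** Section 9.7.1 censors safety and efficacy at the earlier of unblinding and unscheduled vaccine. Section 9.7.2 says that at the general unblinding Cohort 2 will not have completed its schedule, "because the booster vaccinations will not yet have occurred". Applied in full to the booster analyses, that rule would censor every participant before the booster and leave no post-booster safety or efficacy data. The booster analyses therefore need their own rule, and the one written for them excludes instead of censoring.

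**3. Find where the loss could arise.** Under section 9.5, each booster interim is run after the last participant has received that booster and "will include all available safety and immunogenicity data up to 28 days after the vaccination". Someone whose outside vaccine comes after that interim is still counted there. Someone boosted early who is vaccinated outside before the interim is not. For the final analysis the section gives the timing: "The end-of-study analysis will be performed when all included participants have completed the last visit or last booster vaccination follow-up visit". Any booster tabulation made then would apply the exclusion to every outside vaccine up to that point.

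**4. Size, as an illustration only.** The plan's own precision figures come first. Section 9.2 gives upper bounds of 3.9% and <2.5% after zero events in 75 and 120 participants. The one-sided exact bound is 1 − 0.05^(1/n):

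- n = 75: 3.92%
- n = 120: 2.47%

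Both reproduce. The same formula is now applied to a booster group of 30 (Tables 2 and 3), together with the chance of seeing at least one adverse event of 5% incidence, 1 − 0.95^n. The losses of 1, 3 and 6 are assumptions, because the documents give no count.

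| Lost | n | Upper bound after 0 events | Chance of at least one 5% event |
|---|---|---|---|
| 0 | 30 | 9.5% | 78.5% |
| 1 | 29 | 9.8% | 77.4% |
| 3 | 27 | 10.5% | 75.0% |
| 6 | 24 | 11.7% | 70.8% |

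**The case against.** The best defence is that 9.7.2 can be read coherently. The unblinding part of the 9.7.1 rule cannot govern analyses that are to be produced as planned, but the unscheduled-vaccine part can, and it censors by date. On that reading, following the schedule means following it up to the booster being analysed. Section 9.7.2 also refers to Figure 10, which sets out the strategy by scenario and is not visible. The SAP is not at hand either, and either one may supply the timing. This is a plausible account of the intent, but it is not what the text says. The synopsis excludes the participant outright, and no sentence ties the exclusion to the period before the injection.

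A second defence is that restricting to schedule followers is a legitimate choice. Someone boosted at 6 months who takes an outside vaccine before month 12 does miss a scheduled injection. That is a reason to leave the person out of the 12-month analysis. It is not a reason to discard the completed 6-month data.

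The defence is right about weight. The booster interims capture everyone vaccinated outside after them. Section 9.5 does not spell out a repeat booster tabulation at end of study, so disagreement between interim and final tables is possible but not established. Section 9.7.1 also still lists SAEs and AESIs that follow an unscheduled vaccine.

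**Conclusion.** The point stands as a badly worded rule of low severity. Two places in the protocol fix a participant-level exclusion with no time limit. Taken literally, it removes complete booster data because of a later event. It touches an exploratory, descriptive objective and no hypothesis test.

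Three stronger conclusions might be inferred, and the documents support none of them.

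- **That many boosted participants are lost.** The rationale for Amendment 16 names outside vaccination, together with infections, as a main reason why fewer Cohort 2 participants remained than expected. It gives no count among those already boosted at 6 or 12 months.
- **That most booster data are exposed because follow-up runs long past the 28-day window.** The length of follow-up is calendar time. It is not the chance that a participant takes an outside vaccine.
- **That the booster safety results are biased in a known direction.** Nothing shows whether those who go outside reacted more or less to the booster.

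The conclusion assumes that neither Figure 10 nor the SAP limits the timing. If one of them does, what remains is to bring the wording of the synopsis and 9.7.2 into line with it.

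**What to change.** In the synopsis and 9.7.2, state the rule for each booster time point:

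- Exclude from that booster's safety and efficacy analyses only participants whose unscheduled vaccination preceded that injection.
- Keep all others, and censor at the date of any later unscheduled vaccination.
- State that the general unblinding after emergency authorisation does not censor the booster analyses.

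The cost is a clause in two places and a date comparison in the analysis dataset. Section 6.8 already requires the name and date of any outside COVID-19 vaccine to be recorded, so no new data are needed.

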**Figure 8: Participant Enrollment and First Dose Safety Strategy in Cohorts 1 and 3**

C = cohort; DRC = Data Review Committee; PI = principal investigator; SRP = study responsible physician

## Booster Vaccinations in Cohort 2

*Note: For participants at Belgian sites: per Belgian-specific Protocol Amendment 15, this section is no longer applicable as participants aged <65 years enrolled at Belgian sites are not eligible to receive a booster vaccination with Ad26.COV2.S.*

To gain preliminary insight into the safety and immunogenicity of a single booster vaccination, designated participants in Cohort 2 who received Ad26.COV2.S for the single-dose (Cohort 2a) or 2-dose (Cohort 2b) primary regimen will receive a single booster vaccination of Ad26.COV2.S at 6 months or 12 months after completion of the primary regimen, and will receive placebo at the other applicable time point. As a control, a subgroup of participants who received Ad26.COV2.S for the primary regimen will receive placebo at 6 months and 12 months after completion of the primary regimen. In addition, participants who received placebo for the primary regimen will receive placebo at 6 months and 12 months after completion of the primary regimen a ([Table 2](#) and [Table 3](#)). An Ad26.COV2.S dose level of  $5 \times 10^{10}$  vp will be used for the booster vaccination in Cohorts 2a and 2b.

a At the time of unblinding, after EUA or approval in any country and local approval of Protocol Amendment 10, only the Group 5 (placebo only) participants not willing to receive a single dose of  $5 \times 10^{10}$  vp Ad26.COV2.S or another authorized/licensed COVID-19 vaccine will continue Group 5 booster vaccinations in Cohort 2 (refer to Section 8.6).

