### **Unblinding after Protocol Amendment 15 Approval (Ad Hoc Booster Vaccination)**

Following local approval of Amendment 15 by the Health Authority and IEC/IRB, participants in Group 1 and 4 of Cohort 2 will be partially unblinded. After unblinding, enrolled eligible participants from Groups 1 and 4 of Cohort 2 will be offered a single ad hoc booster dose of  $5 \times 10^{10}$  vp Ad26.COV2.S. If willing to receive, they will discontinue from participation in their current booster schedule. Refer to Sections 7.5 and 8.7 for more details.

Statistical analysis of data obtained from the point of unblinding is outlined in Section 9.8.

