#### **9.4.2. Primary Endpoints**

##### **Safety Endpoints**

No formal statistical testing of safety data is planned. Safety data will be analyzed descriptively by vaccine group. In addition, for selected tables, tabulations pooled by vaccine dose will also be provided. All safety analyses will be made on the FAS.

---

a If a participant would be vaccinated out of window due to a study pause (per Section 6.9), this will not by default be a reason for excluding this participant from the PPI. A sensitivity analysis might also be performed. Further details will be described in the Statistical Analysis Plan.

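### Post-booster safety drops only participants unblinded at their own request, although Group 5 crossover decliners and Groups 1/4 ad hoc booster decliners also know their injection is placebo

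*Protocol*

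**What the plan says.** Section 9.7.2 keeps the Cohort 2 booster analyses going after the Amendment 10 unblinding and defines who is in them: "The analyses will include all available participants who have followed the vaccination schedules as per the study design (ie, did not receive an unscheduled vaccination". It then adds one exclusion based on unblinding, "the post-booster safety or efficacy analyses will not include participants who were unblinded at their own request", and explains it as "implying they would know in advance whether they would receive active vaccine or placebo at each of the booster time points". Section 9.6 states the same rule and presents it as the sole departure from the general approach.

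Section 8.6 describes what happens under Amendment 10: "All currently enrolled participants will be contacted by the study site to inform them whether they received active vaccine or placebo only". Section 9.7.2 places this before the Cohort 2 boosters, "because the booster vaccinations will not yet have occurred". Under Tables 2 and 3, Group 5 receives placebo at every booster time point. Those who want neither the crossover dose nor an outside vaccine "will continue Group 5 booster vaccinations in Cohort 2" (Section 4.1, footnote to the Cohort 2 booster text; Section 8.6 agrees).

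Section 6.3 describes Amendment 15: "participants in Group 1 and 4 of Cohort 2 will be partially unblinded". Tables 2 and 3 give both groups placebo at the first and second boosters, and footnote d, for the US, keeps those who decline the ad hoc booster on their existing schedule. Section 9.8 adds receipt of the ad hoc booster as a reason for censoring and says nothing about those who decline it.

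**The concern.** The exclusion rests on a stated principle: someone who knows whether the injection is active or placebo should not contribute to a blinded safety comparison. The rule then applies that principle to one route of unblinding and leaves out two others that give the same knowledge.

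Solicited events are self-reported in a 7-day diary (Section 8.3.2), which makes them the safety data most open to expectation. Section 4.2 gives reduced bias in data collection as the purpose of blinding. If part of the placebo experience comes from people who know they had placebo, the difference between active and placebo boosters may reflect that knowledge as well as the vaccine. A reader of the tables could not tell which reports were which.

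**Working it through.** **Figures in the plan.** The protocol gives no figure on this point. Its only sample-size figures (Section 9.2) reproduce: 1 − 0.05^(1/75) = 3.9% and 1 − 0.05^(1/120) = 2.5%. They do not bear on the matter.

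**Who knows the content of a booster before it is given?**

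| Participants | What they are told | What Tables 2 and 3 then imply | Treatment in the analysis |
|---|---|---|---|
| Unblinded at own request | Likely full assignment (9.6) | Content of every booster | Excluded |
| Group 5, decline crossover and outside vaccine | Placebo only (8.6) | Placebo at every booster | Included |
| Groups 1/4, decline ad hoc booster, dosed after local Amendment 15 unblinding | Identified as Group 1 or 4 (6.3) | Placebo at the second booster | Included |
| Groups 2/3 | No formal disclosure of booster group | At the second booster, Group 2 placebo and Group 3 active | Included |

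In the third row, the offer itself settles the content. Section 8.7 makes Group 5 and Groups 2 and 3 ineligible, so within Cohort 2 only Groups 1 and 4 can be offered the ad hoc booster. The two groups differed only at the 24-month dose (26 months in Cohort 2b), which Amendment 16 removed.

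**Does the general censoring rule remove them?** Section 9.7.1 censors safety at unblinding, and Section 9.7.2 says the same strategy applies to Cohort 2. Taken literally for boosters, it would delete all the booster safety data, because everyone is unblinded as to active or placebo-only before boosting. Section 9.7.2 avoids this by having the booster analyses go ahead as planned in everyone who stayed on schedule. That inclusion rule also keeps the second and third rows.

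**Planned upper bounds (Tables 2 and 3, Cohorts 2a and 2b together).**
- Groups 1 to 4: 30 + 30 = 60 each. Group 5: 15 + 15 = 30. Total: 4 × 60 + 30 = 270.
- Placebo recipients at the first booster (Groups 1, 3, 4, 5): 3 × 60 + 30 = 210. Group 5 share: 30/210 = 14%.
- Placebo recipients at the second booster (Groups 1, 2, 4, 5): also 210. Groups 1, 4 and 5 together: 150/210 = 71%.

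**Range with attrition (assumed; the document gives no retention figures).** Suppose a fraction f of those 150 stays on schedule, all of Group 2 (60) stays, and every second booster in Groups 1 and 4 follows local unblinding. The aware share of second-booster placebo recipients is 150f/(150f + 60):
- f = 10%: 15/75 = 20%
- f = 25%: 37.5/97.5 = 38%
- f = 50%: 75/135 = 56%

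**Timing for Groups 1 and 4.** Amendment 15 is dated 7 October 2021. Assume no Cohort 2 dosing before Amendment 6 (19 September 2020). The Cohort 2b second-booster window then opens at Day 422 − 21 = Day 401, which is 24 October 2021, or 21 October if the second dose came 3 days early. In Cohort 2a, anyone first dosed after 7 October 2020 has a 12-month target (Day 366) after 7 October 2021. The second booster is therefore the one exposed. How many injections followed local approval cannot be determined.

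**The case against.** Several points on the other side stand. Safety is tabulated by vaccine group, so Group 5 has its own column. For that group the problem is comparison between columns, and mixing within a column arises in pooled Groups 1 and 4 (Section 9.5). Open-label ad hoc doses are censored from the main analyses and reported separately (Section 9.8), and recipients of unscheduled vaccines are left out, so known-active injections by those routes are not mixed in. Footnote d is limited to the US, and at Belgian sites the Cohort 2 booster section no longer applies. The objective is exploratory, with no hypothesis test.

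It can also be argued that Section 9.8, by referring to censoring by date of unblinding, already removes those who decline the ad hoc booster. At most this makes the text ambiguous, since the same reading would remove the planned booster analyses altogether. Section 9.8 defers detail on the ad hoc booster analysis to the statistical analysis plan, but the exclusion rule itself is fixed in Sections 9.6 and 9.7.2.

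A reader might infer three stronger points that the protocol does not support:
- **Groups 2 and 3 learn their content by not being offered the ad hoc booster.** They do not: at the second booster one group gets placebo and the other active. A participant may also not be offered it because of a recent vaccination, a recent infection or medical history (Section 8.7).
- **Every injection after Amendment 15 should therefore leave the blinded set.** That would remove Groups 2 and 3, who still cannot tell active from placebo, and on the dates above could empty the Cohort 2b second-booster comparison.
- **Excluding self-unblinded participants hides serious events and breaches "All safety analyses will be made on the FAS".** Section 9.7.1 lists SAEs and AESIs reported after unblinding, and Section 9.7.2 carries that strategy to Cohort 2. The full-analysis-set sentence is a general rule with specific provisions after it.

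**Conclusion.** The point holds in a limited form. The protocol's own reason for excluding self-unblinded participants applies equally to Group 5 members who decline crossover and continue placebo boosters, and to US Groups 1 and 4 members who decline the ad hoc booster and receive a scheduled injection after local Amendment 15 unblinding. Neither set is excluded or separated.

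The planned ceilings are 30 and 120. Actual numbers will be lower by an amount the protocol does not give, and the figure for Groups 1 and 4 also depends on local approval dates. The direction of any bias is not established. The effect is confined to the interpretation of exploratory, descriptive post-booster reactogenicity and unsolicited events; no primary or secondary endpoint of the main study is touched. It does not make the booster comparison as a whole open-label, and the protocol nowhere says the results will be presented as fully blinded. It is worth correcting because the correction is cheap.

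**What to change.** In Sections 9.6, 9.7.2 and 9.8, define a flag for each booster injection: had the participant, before dosing, been told information that fixes its content?

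- Present solicited and unsolicited post-booster events for aware Group 5 injections and aware Groups 1/4 injections in separate open-label columns.
- As blinded placebo control, use only injections given to participants not yet unblinded to content. At the first booster these are in Groups 1, 3 and 4. At the second they are in Group 2, and in Groups 1 and 4 where dosing preceded local Amendment 15 unblinding.
- Keep Groups 2 and 3 in the blinded set, flagging doses given after Amendment 15.
- Leave the listing of SAEs and AESIs after unblinding as it is.

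The cost is a wording change, one analysis flag and extra table columns; no treatment or visit changes. The downside is a smaller blinded placebo control at the second booster. If every Groups 1/4 injection there followed local unblinding, it would reduce to Group 2, planned at 60 (30 in each sub-cohort).
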